8.11.3 Follow-up of AEs and SAEs

After the initial AE/SAE report, the investigator is required to proactively follow each subject at subsequent visits/contacts. All AEs, including SAEs will be followed until resolution, stabilization, the event is otherwise explained, or the subject is lost to follow-up (as defined in [Section 7.3](#)). Further information on follow-up procedures is provided in [Appendix 2](#).

8.11.4 Regulatory Reporting Requirements for SAEs

The Sponsor has a legal responsibility to notify both the local regulatory authority and other regulatory agencies about the safety of a study medication under clinical investigation. The sponsor will comply with country-specific regulatory requirements relating to safety reporting to regulatory authorities, IRB/IEC, and investigators.

Investigators who receive a safety report describing an SAE or other safety information (eg, summary or listing of SAEs) from the Sponsor will review and then file it with the applicable reference safety information and will notify the IRB/IEC, if appropriate, according to local requirements. For this study, the reference safety information for the study medication, ENTO, is the Investigator's Brochure (Edition 11.0). For all chemotherapy agents (cytarabine, daunorubicin, idarubicin), the reference safety information is the local health authority-approved prescribing information.

Safety reports must be prepared for SUSARs in accordance with local regulatory requirements and Sponsor policy and forwarded to study investigators, as necessary.

8.11.5 Reporting Pregnancy

If a female patient or the partner of a male patient becomes pregnant while receiving or within 3 months of discontinuing study treatment, a pregnancy report form must be completed and submitted to the sponsor within 24 hours of learning of the pregnancy (after obtaining the necessary signed informed consent from the female partner of a male patient) to facilitate outcomes follow-up.

While pregnancy itself is not considered an AE, any pregnancy complications (eg, spontaneous abortion, fetal death, stillbirth, congenital anomalies, ectopic pregnancy) or elective termination of a pregnancy for medical reasons will be reported as a SAE. For pregnancies taken to term, details on the status of the mother and the child will be forwarded to the sponsor, with follow-up generally no longer than 6 to 8 weeks after the delivery date. Any female participant who becomes pregnant while participating in the study will discontinue study treatment but may continue to be followed for leukemic progression/relapse, first salvage therapy and survival.

Any post-study pregnancy-related SAE considered by the investigator at least possibly related to the study treatment will be reported to the Sponsor as described in [Section 8.11.4](#). While the investigator is not obligated to actively seek this information from former study subjects or pregnant female partners of male subjects, he or she may learn of an SAE through spontaneous reporting.

CONFIDENTIAL

Protocol KB-ENTO-3001 v4.0

(Amendment 3.0)

9.0 Statistical Considerations

9.1 Statistical Hypotheses

The primary efficacy endpoint is MRD negative CR rate after Chemotherapy Cycle 2.

The hypothesis of interest is a two-sided test of superiority comparing ENTO to placebo.

$$H_0: p_{\text{placebo}} = p_{\text{ENTO}} \text{ vs } H_{11}: p_{\text{placebo}} \neq p_{\text{ENTO}},$$

where p_{placebo} is the proportion of subjects in the placebo group with MRD negative CR after Chemotherapy Cycle 2, and p_{ENTO} is the proportion of subjects in the ENTO group with MRD negative CR after Chemotherapy Cycle 2.

9.2 Sample Size Determination

Based on a completed study of newly diagnosed AML subjects treated with ENTO, it is anticipated that 87% of *NPM1*-m subjects will achieve CR ([Walker 2020](#)). Based on analysis of a historical dataset from the Cancer and Leukemia Group B Alliance ([Mims et al, 2021](#)) showing a 68% CR rate in 107 *NPM1*-mutated/*FLT3-ITD* negative patients ≥ 60 years of age treated with 7+3 induction, a conservative estimate of 70% CR rate for placebo is assumed for sample size determination. The MRD negative rate among placebo subjects achieving CR is assumed to be 60% ([Ivey et al, 2016](#)). Alternatively, it is hypothesized that 80% of subjects with CR receiving ENTO will be MRD negative. A sample size of 90 subjects per group (total of 180 subjects) will provide $> 97\%$ power to detect a difference in the MRD negative CR rate of 28% (87% x 80% = 70% for ENTO vs 70% x 60% = 42% for placebo) with a 2-sided alpha level of 0.05 (PASS 2008: Two sample test of Proportion Module). Up to 10% over enrollment is allowable in order to account for technical or logistical barriers (eg. inadequate bone marrow aspirate or poor sample quality) related to the ascertainment of MRD status in patients who achieve CR post-Chemotherapy Cycle 2.

Assuming the two-year EFS rate for the control group is 63% (hazard rate of 0.231), a total of 124 events (70 in the placebo arm, 54 in the ENTO arm) would be sufficient to provide 80% power to detect a hazard ratio of 0.6 for EFS (PASS 2008: log rank tests (Lakatos) [Hazard Rate] module) assuming 2-sided alpha = 0.05 and a total study duration of 60 months.

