For subjects with < 5% residual blasts post-Induction Cycle 1, Consolidation Cycle 1 will consist of Chemotherapy Cycle 2. For patients with ≥5% residual blasts post-Induction Cycle 1, Induction Cycle 2 will consist of Chemotherapy Cycle 2 ([Synopsis Table 1](#)) with consolidation beginning thereafter. All subjects are eligible to receive up to 3 cycles of high dose cytarabine after Chemotherapy Cycle 2.

All subjects will undergo an End-of-Study Treatment Visit 30 ± 7 days after the last study treatment (either ENTO/placebo or chemotherapy, whichever is later) or prior to initiation of follow-on therapy (eg, maintenance therapy, HSCT), if sooner than 30 ± 7 days after last study treatment.

All subjects regardless of their post-remission status will be followed monthly for 3 months after the End-of-Study Treatment Visit and thereafter at least once every 3 months for progression/relapse, first salvage therapy, and survival until study termination. Unscheduled study visits at other time points are permitted in the setting of suspected leukemic recurrence or for evaluation and management of post-treatment sequelae.

Number of Participants:

Approximately 180 subjects will be randomized. A sample size of 90 subjects per group will provide > 97% power to detect a difference in the MRD negative CR rate of 28% (87% CR rate x 80% MRD negativity among patients who achieve CR) = 70% for ENTO vs 70% x 60%, respectively = 42% for placebo) with a 2-sided alpha level of 0.05 (PASS 2008: Two sample test of Proportion Module). Up to 10% over enrollment is allowed in order to account for technical or logistical barriers (eg. inadequate bone marrow aspirate or poor sample quality) related to the ascertainment of MRD status in patients who achieve CR post-Chemotherapy Cycle 2.

Study Duration:

The study will be completed when all enrolled subjects either relapse, die, or after the last subject enrolled completes 5 years of follow-up, whichever is earliest.

Statistical Analysis:

Detailed methodology for summary and statistical analyses of the data collected in this study will be documented in a Statistical Analysis Plan (SAP).

CONFIDENTIAL

Protocol KB-ENTO-3001 v4.0 Global
(Amendment 3.0 Global)

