All 53 subjects across the Phase 1b and Phase 2 portions of the study were considered evaluable for efficacy. Thirty-seven subjects (70%) subjects achieved a CR or CR with incomplete recovery of neutrophil or platelet counts (CRI), including 13 of 15 *NPM1*-mutated subjects (87%). Among 10 subjects with rearrangement of the *MLL* gene (*MLL*-r), a mutation also associated with high baseline expression of *HOXA9* and *MEIS1*, 9 (90%) experienced a CR or CRI, including one patient who achieved a cytogenetic and morphologic CR after the ENTO monotherapy lead-in period. In contrast, the CR + CRI rate for the remaining 28 *MLL* and *NPM1* wild-type subjects was 54%. An exploratory retrospective analysis of *HOXA9* and *MEIS1* mRNA levels at baseline was performed for 34 subjects with available samples. Subjects with expression levels of *HOXA9/MEIS1* above the median for the overall group experienced superior overall survival compared to those with expression levels below the median (hazard ratio, 0.32; 95% confidence intervals, 0.100 to 0.997, p = 0.038) ([Figure 3](#)). Despite the small sample size and single-arm design of this study, higher CR/CRI rates in *NPM1*-mutated subjects and superior overall survival in the *HOXA9/MEIS1* high expressing subset are consistent with the hypothesis that SYK is a therapeutic dependency in this subset of AML and warrants further study.

The combination of ENTO with 7 + 3 induction and high dose cytarabine consolidation was generally well-tolerated with skin rash, liver transaminase elevations, and indirect hyperbilirubinemia being the most commonly reported ENTO-related toxicities ([Section 2.4](#); [Walker 2020](#)).

CONFIDENTIAL

Protocol KB-ENTO-3001 v4.0 Global
(Amendment 3.0 Global)**Figure 3: Overall Survival in Newly Diagnosed AML Patients Treated With 7+3 and ENTO Induction.**

Abbreviations: AML, acute myeloid leukemia; ENTO, entospletinib

Note: K-M curve in gray represents all 34 subjects. Light blue line represents subjects with *HOXA9/MEIS1* mRNA expression above the median level of expression (N = 17). The pink line is subjects with expression below the median (N = 17). OS is censored on the last date the subject was known to be alive ([Walker 2020](#)).

Phase 2 Study of ENTO in *NPM1*-mutant/*FLT-3* Wild -Type AML Patients (Study BAML-16-001-S6)

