3.0 Objectives and Endpoints

Objectives	Endpoints
Primary	

 To evaluate the efficacy of ENTO compared to placebo when added to chemotherapy in previously untreated NPM1-m AML, as defined by the rate of molecularly defined measurable residual disease (MRD). 	
 MRD negative CR rates after completion of 2 cycles of chemotherapy plus either ENTO or placebo. 
Note: MRD negative CR requires CR as defined by ELN 2017 criteria (with minor modification for neutrophil and platelet count thresholds as defined by the International Working Group [IWG]) as assessed by study site investigators, and MRD negativity (<0.01%) in bone marrow as measured by a molecular NPM1-m assay (eg, next generation sequencing) in a central laboratory upon recovery of peripheral blood counts following completion of 2 cycles of chemotherapy (ie, no later than Day 42 of Cycle 2).

Secondary	

 To evaluate the efficacy of ENTO compared to placebo when added to chemotherapy in previously untreated NPM1-m AML, as defined by relapse-free, event-free, and overall survival. 	
 Event-free survival, defined as the time from randomization to the earliest occurrence of induction treatment failure, relapse from CR, or death from any cause. 
Note: Induction treatment failure is failure to achieve morphological CR after completion of the last cycle of induction chemotherapy (no later than Day 42 of the last cycle of induction).
 
 Relapse-free survival, defined as the time from CR until relapse or death from any cause as assessed by study site investigators. Overall survival defined as the time from randomization until death from any cause.

 To evaluate the efficacy of ENTO compared to placebo when added to chemotherapy in previously untreated NPM1-m as defined by CR rate. 	
 CR rates after 2 cycles of chemotherapy, as defined by ELN 2017 criteria (with minor modification for neutrophil and platelet count thresholds as defined by the IWG) as assessed by study site investigators.

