Cytarabine	1.0 g/m ² , BID Days 1-6	1.0 g/m ² , BID Days 1-6
Anthracycline	Daunorubicin, 60 mg/m ² slow IV push, Days 1-3 OR Idarubicin, 12 mg/m ² slow IV push, Days 1-3	N/A

Abbreviations: BID, twice daily; IV, intravenous; N/A, not administered.

^a Subjects who are candidates for continuous infusion of cytarabine in Cycle 1 at doses higher than 100 mg/m²/day are ineligible.

Subjects will undergo bone marrow examination no later than Day 42 of Induction Cycle 1 for assessment of response. Subjects with $\geq 5\%$ residual leukemic blasts in bone marrow will receive Induction Cycle 2 as outlined in [Table 4](#), which may be administered prior to blood count recovery. Subjects with $< 5\%$ residual blasts will receive Consolidation Cycle 1 as outlined in [Table 5](#) upon recovery of peripheral blood counts (absolute neutrophil count [ANC] $> 1.0 \times 10^9/L$; platelet count $> 100 \times 10^9/L$). After completion of Induction Cycle 2 or Consolidation Cycle 1 (hereafter referred to collectively as Chemotherapy Cycle 2), subjects will undergo bone marrow examination for assessment of remission status at the investigative site (bone marrow biopsy is mandated if sufficient or adequate aspirate cannot be obtained, eg, due to dry tap, hemodilution or hypocellularity). Bone marrow examination should await recovery of ANC to $> 1.0 \times 10^9/L$ and platelet count to $> 100 \times 10^9/L$ no later than Day 42 of Chemotherapy Cycle 2, unless leukemic progression is suspected. Subjects who achieve or remain in morphologic CR after Chemotherapy Cycle 2 will undergo MRD assessment in peripheral blood and bone marrow aspirate in a central laboratory designated by the Sponsor. Subjects who have not achieved morphologic CR after the last cycle of induction (whether it be Induction Cycle 1 or Induction Cycle 2) will be deemed treatment failures. [Figure 4](#) provides a schematic representation of the study treatment plan from Cycle 1, Day 1 through completion of Chemotherapy Cycle 2.

Figure 4 Treatment Phase: Cycle 1, Day 1 through Completion of Chemotherapy Cycle 2:

* Following recovery of ANC to $>1.0 \times 10^9 / \text{L}$ and platelet count to $>100 \times 10^9 / \text{L}$
 BMA, bone marrow aspirate; MRD, measurable residual disease

Subjects who achieve MRD negative CR post-Chemotherapy Cycle 2 will undergo retrospective MRD assessments in peripheral blood every 3 months until morphologic relapse.

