5.0 Study Population

5.1 Inclusion Criteria

Participants are eligible to be included in the study only if all the following criteria apply:

1. Adults 18 to 74 years with previously untreated *de novo* AML, AML with MDS features, or therapy-related AML, who are candidates for intensive induction therapy.
2. *NPM1*-mutated disease documented in a local or the Sponsor's central testing facility.

Note: Subjects with local test results for *NPM1*-m (and/or *FLT3* mutational status) may enroll, provided appropriate samples are sent to the Sponsor's central testing facility for *NPM1*-m companion diagnostic development (see [Section 4.1](#)).

3. Eastern Cooperative Oncology Group Performance Status (ECOG PS) score of 0, 1, or 2.
4. Adequate hepatic and renal function defined as:
 - a. Serum aspartate aminotransferase (AST) and alanine aminotransferase (ALT) < 2.5 times the upper limit of normal (ULN), except those with hepatic involvement by AML, as documented by either computed tomography (CT) or ultrasound, in whom levels of AST and ALT < 5 times ULN are acceptable; total bilirubin < 1.5 times ULN unless elevated due to Gilbert's Disease or hemolysis.
 - b. Calculated creatinine clearance > 40 mL/min or serum creatinine < 1.5 times ULN.
5. Prothrombin time (PT), activated partial thromboplastin time (aPTT), and international normalized ratio (INR) $\leq 1.5 \times$ ULN unless receiving therapeutic anticoagulation. *Note:* Transition from a Vitamin K or Factor Xa antagonist to a low-molecular weight heparin preparation is recommended prior to the start of induction chemotherapy (see [Appendix 8](#) for guidelines on anticoagulation management).
6. Left ventricular ejection fraction $\geq 45\%$ confirmed by echocardiogram (ECHO) or multi-gated acquisition (MUGA) scan.
7. Negative serum β -HCG test in women of childbearing potential (WOCBP).
8. For WOCBP, willingness to abstain from heterosexual intercourse OR to use a protocol-recommended method of contraception from 7 days prior to C1D1 throughout the study treatment period and for 90 days following the last dose of ENTO/placebo or as recommended in the prescribing information for other co-administered study drugs (whichever is later). See [Appendix 3](#) for contraceptive guidance.

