10.4 Appendix 4: Response Criteria

Complete Response (CR)*

CR requires all the following:

- Bone marrow blasts < 5%
- Absence of circulating blasts and blasts with Auer rods
- Absence of extramedullary disease (ie, leukemia outside of bone marrow confirmed by biopsy)
- Absolute neutrophil count > $1.0 \times 10^9/L$ (1000/ μL)
- Platelet count > $100 \times 10^9/L$ (100,000/ μL)

*Note: *MRD positive or unknown*

Complete Response with Hematologic Improvement (CRh)**

CRh requires all the CR criteria, except for residual thrombocytopenia and/or neutropenia and is defined as:

- Bone marrow blasts < 5%
- Absence of circulating blasts and blasts with Auer rods
- Absence of extramedullary disease
- Absolute neutrophil count > $0.5 \times 10^9/L$ (500/ μL)
- Platelet count > $50 \times 10^9/L$ (50,000/ μL)

Complete Response with Incomplete Blood Count Recovery (CRi)**

CRi requires all the CR criteria, except for residual neutropenia or thrombocytopenia and is defined as:

- Bone marrow blasts < 5%
- Absence of circulating blasts and blasts with Auer rod
- Absence of extramedullary disease
- Absolute neutrophil count $\leq 1.0 \times 10^9/L$ (1000/ μL) or platelet count $\leq 100 \times 10^9/L$ (100,000/ μL)

*Note: **If subjects meet criteria for both CRh and CRi, they should be classified as CRh*

Morphologic Leukemia Free State (MLFS)***

- Bone marrow blasts < 5%
- Absence of blasts with Auer rods
- Absence of extramedullary disease
- No hematologic recovery required

*Note: *** Marrow should not be merely “aplastic”; at least 200 cells should be enumerated or cellularity on bone marrow biopsy should be at least 10% of normal.*

Partial Response (PR)

PR meets all hematologic criteria of CR:

- Absolute neutrophil count > $1.0 \times 10^9/L$ (1000/ μL)

CONFIDENTIAL

Protocol KB-ENTO-3001 v4.0

(Amendment 3.0)

- Platelet count $> 100 \times 10^9/L$ ($100,000/\mu L$), and
- Residual bone marrow blast percentage of 5% to 25%
- Reduction of bone marrow blast percentage by $\geq 50\%$ compared with pretreatment

Stable Disease (SD)

Absence of MRD negative CR, CR, CRh, CRi, PR, MLFS and criteria for PD not met.

Progressive Disease (PD)

Evidence for an increase in bone marrow blast percentage and/or circulating blast counts as defined by at least one of the following:

- $> 50\%$ increase in bone marrow blasts over baseline (a minimal absolute 15% increase is required in cases with $< 30\%$ blasts at baseline), or

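### The 87% entered as the entospletinib CR rate is reported in Section 2.2 as CR or CRi (13 of 15), so the stated power of over 97% sets a CR-or-CRi rate against a CR rate

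*Protocol*

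**What the plan says.** Section 9.2 takes its ENTO response rate from a completed study of newly diagnosed AML: "it is anticipated that 87% of *NPM1*-m subjects will achieve CR". SAP Section 4.2 repeats the statement, and the Synopsis writes the product as "87% CR rate x 80% MRD negativity among patients who achieve CR". For control, Section 9.2 cites a 68% CR rate in 107 patients aged 60 or over and adds that "a conservative estimate of 70% CR rate for placebo is assumed for sample size determination". Multiplying by MRD-negative fractions of 80% and 60% gives 70% vs 42%, and 90 subjects per group are said to give more than 97% power at two-sided 0.05.

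Section 2.2 describes the completed study's result differently: "Thirty-seven subjects (70%) subjects achieved a CR or CR with incomplete recovery of neutrophil or platelet counts (CRI), including 13 of 15" NPM1-mutated subjects, which it shows as 87%.

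The endpoint is defined in Section 3.0: "MRD negative CR requires CR as defined by ELN 2017 criteria", with modified count thresholds. Appendix 4 keeps the two categories apart: "CRi requires all the CR criteria, except for residual neutropenia or thrombocytopenia and is defined as" a neutrophil count of 1.0 × 10⁹/L or lower, or a platelet count of 100 × 10⁹/L or lower, with marrow blasts under 5%. A subject in CRi therefore fails a CR count threshold.

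**The concern.** The same 87% has two labels. Where it is reported it covers CR and CRi; where it enters the power calculation it is called CR. The primary endpoint does not count CRi, and the control rate beside it is stated as CR. If any of the 13 responders had CRi, the ENTO input is too high for this endpoint while the control input is not affected in the same way, so the planned difference and the power are both overstated. Because the estimate rests on 15 subjects, moving one responder shifts the rate by almost 7 points (1/15 = 6.7%). A reader of Section 9.2 or SAP Section 4.2 alone would take 87% as an observed CR rate for this endpoint.

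**Working it through.** **Inputs.** n = 90 per group, two-sided alpha 0.05, MRD-negative fractions among CR of 80% (ENTO) and 60% (placebo), placebo CR 70% (Section 9.2); 13 of 15 (Section 2.2).

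**Formula.** Normal approximation for two proportions, with p̄ = (p1 + p2)/2.

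- Pooled: power = Φ{[(p1 − p2) − 1.96 √(2p̄(1 − p̄)/n)] / √(p1(1 − p1)/n + p2(1 − p2)/n)}
- Unpooled: power = Φ{(p1 − p2)/√(p1(1 − p1)/n + p2(1 − p2)/n) − 1.96}

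**Step 1: the plan's own figure.** p1 = 0.70, p2 = 0.42, p̄ = 0.56. The null standard error is 0.0740 and the alternative standard error is 0.0710.

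- Pooled: (0.28 − 1.96 × 0.0740)/0.0710 = 1.90, power 97.1%.
- Unpooled: 0.28/0.0710 − 1.96 = 1.98, power 97.6%.
- Without rounding, 0.87 × 0.80 = 0.696, and the pooled power is 96.7%.

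The stated figure reproduces; the rounding is immaterial.

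**Step 2: precision of the source.** 13/15 = 86.7%; the exact (Clopper-Pearson) 95% interval is 59.5% to 98.3%.

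**Step 3: what the label can change.** The CR-only count is 13 or fewer.

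- If none of the 13 was CRi, 87% stands as a CR rate and Step 1 is unchanged.
- If one was CRi (assumption), ENTO CR is 12/15 = 80% and p1 = 0.80 × 0.80 = 0.64. With p2 = 0.42, p̄ = 0.53 and standard errors of 0.0744 and 0.0726, pooled (0.22 − 1.96 × 0.0744)/0.0726 = 1.02, power 84.7%; unpooled 85.8%.

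One reclassified subject thus costs about 12 points (96.7% − 84.7%, both pooled and unrounded).

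**Step 4: sensitivity grid.** Pooled power, unrounded products, 90 per arm. All rates other than those entered are illustrative.

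| ENTO CR | Placebo CR 65% | 70% | 75% | 80% |
|---|---|---|---|---|
| 87% | 98.8% | 96.7% | 92.2% | 84.3% |
| 80% | 92.5% | 84.7% | 72.9% | 58.1% |

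**The case against.** The strongest reply is that no numerical error can be shown. Nothing in the documents says that any of the 13 was CRi. This trial also allows time for counts to recover: "Bone marrow examination should await recovery of ANC to" the CR thresholds, up to Day 42 of Chemotherapy Cycle 2 (Section 4.1), so a CRi in the completed study need not have been a non-CR here. Both points stand, and they limit the claim to a mislabelled input whose effect may be nil. They do not justify printing a CR-or-CRi rate as CR: Section 9.2 neither makes the recovery argument nor says that the two rates are taken as equal.

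A reader might go further in three ways.

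- **That the power figure is wrong or the trial was underpowered.** The documents do not support this. The figure is right for 70% vs 42%, Section 9.2 ties it to those rates, and the 84.7% rests on an assumption.
- **That the 70% placebo rate is wrong or its basis hidden.** Section 9.2 itself states that the source covers ages 60 and over, and 70% is conservative against the cited 68%. The trial enrols "Adults 18 to 74 years with previously untreated *de novo* AML, AML with MDS features, or therapy-related AML", which is broader, but the protocol's other rates point both ways: 86 to 88% in favourable-risk NPM1-mutated disease, 66.3% with adverse cytogenetics (both Section 2.4), and a 65% null hypothesis for composite CR (Section 2.2). Each is a subset or a different response definition; none shows 70% to be wrong.
- **That the 76% interim rate in Section 2.4 should replace 87%.** It would give 71.7% power (pooled), but it is itself a composite rate, from 25 patients in another study, and says nothing about how the 13 responders divide.

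Finally, the SAP records termination with 15 randomized subjects (Section 4.2), no formal testing (Section 4.1) and no analysis of the protocol's primary or secondary efficacy endpoints (Section 6.4). That settles the severity, not the label.

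**Conclusion.** The point holds as a labelling error in a design input. The Synopsis, Protocol Section 9.2 and SAP Section 4.2 call 87% a CR rate; Section 2.2 shows it to be CR or CRi in 13 of 15. It is multiplied into an endpoint that requires CR and compared with a control rate stated as CR. The size is unknown from the documents: no loss of power if none of the 13 was CRi, and 84.7% (pooled; 85.8% unpooled) if one was. Those figures assume 90 per arm, MRD-negative fractions of 80% and 60%, and placebo CR of 70%. Severity is minor, because only the design record is affected and no result depends on it.

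**What to change.** In the Synopsis, Protocol Section 9.2 and SAP Section 4.2, label 87% as CR or CRi (13/15). Look up the CR-only count among the 15 in the completed study, use it in place of 87%, and restate the power if it differs. If the count cannot be obtained, state that the CR-only rate is assumed equal to the CR-or-CRi rate. No edit is needed on the age limit of the placebo source or on the power being conditional on 70% vs 42%, since Section 9.2 already gives both. A sensitivity table is optional; the grid above can be used as it stands.

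The cost is one look-up and a short text change in three places. Enrolment, data and analyses are unchanged.

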4.3 End of Study Definition

The study will be completed when all enrolled subjects either relapse, die, or after the last subject enrolled completes 5 years of follow-up, whichever is earliest.

CONFIDENTIAL

Protocol KB-ENTO-3001 v4.0 Global
(Amendment 3.0 Global)

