9.4.3 Secondary Endpoint(s)

The secondary endpoint variables and their population level summary measures will be described in each of the following sections. The evaluation of the population for the trial, treatments of interest, and the possible intercurrent events are as described in [Section 9.4.2.1](#). All secondary endpoints will include death as part of definition of the variable. Intercurrent events of additional leukemic therapy and premature study treatment discontinuation will be ignored for the primary evaluation of these endpoints. Additional information on the handling of missing data and sensitivity analyses will be detailed in the SAP.

CONFIDENTIAL

Protocol KB-ENTO-3001 v4.0

(Amendment 3.0)

Event-free survival

Event-free survival (EFS) is defined as time from randomization to the earliest of induction treatment failure (ITF), relapse for those who achieve CR, or death from any cause. ITF is failure to achieve morphological CR after completion of the last cycle of induction chemotherapy (no later than Day 42 of the last cycle of induction). Subjects who experience ITF will be treated as events at Day 1.

Subjects who do not experience an event (ITF, relapse from CR, or death) will be censored at their last study evaluation at which they were relapse free. Event-free survival will be estimated using the method of Kaplan-Meier (K-M) and summarized by treatment group. Differences between the treatment groups will be assessed with the log rank test stratified by age (<60 vs \geq 60 years) and choice of anthracycline in induction (daunorubicin vs idarubicin). The population level summary measure will be the adjusted hazard ratio as calculated from a Cox proportional hazards model with effects for treatment, age, and choice of anthracycline in induction.

Relapse free survival

For subjects who achieve CR, relapse free survival (RFS) is defined as the time from CR to morphologic relapse as assessed by the study site investigator or death from any cause, whichever comes first. Subjects who do not experience a relapse or death will be censored at the last study evaluation at which they were relapse free. RFS will be estimated using the K-M method and summarized by treatment group. The population level summary measure will be the adjusted hazard ratio as calculated from a Cox proportional hazards model with effects for treatment, age, and choice of anthracycline in induction.

Overall survival

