9.5.2 Blinded Review of EFS Events

Prior to unblinding for the primary endpoint analysis, the sponsor will review the number of EFS events achieved. If the rate of events is slower than anticipated, the sponsor may propose an increase in sample size in order to achieve the events necessary for the confirmatory analysis of EFS. The increase will be based on the original sample size assumptions for hazard ratio and two-year EFS rate of the placebo group. The proposed sample size increase will be shared with the DMC and appropriate regulatory agency prior to implementation. Given that the review will be conducted in a blinded fashion, no adjustment for Type 1 error is proposed.

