9.5.4 EFS Analysis

A final EFS analysis will be conducted once the pre-specified number of events have been reported and the resulting database is cleaned and locked.

CONFIDENTIAL

Protocol KB-ENTO-3001 v4.0

(Amendment 3.0)

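### Section 9.2's total study duration of 60 months does not fit its 124 EFS events: its own hazards give at most about 107 expected events from 180 subjects in that time

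*Protocol*

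**What the plan says.** Protocol Section 9.2 plans 180 subjects, 90 per arm, with up to 10% over-enrollment. For EFS it assumes 63% event-free at two years on placebo, which it converts to a hazard of 0.231, and states that "a total of 124 events (70 in the placebo arm, 54 in the ENTO arm) would be sufficient to provide 80% power" for a hazard ratio of 0.6, "assuming 2-sided alpha = 0.05 and a total study duration of 60 months". The EFS sentence gives no sample size, accrual period or dropout rate of its own. SAP Section 4.2 repeats the statement.

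Three other places bear on timing:

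- Section 4.3 ends the study when all subjects have relapsed or died, or "after the last subject enrolled completes 5 years of follow-up, whichever is earliest".
- Section 9.5.4 makes the analysis event-driven: "A final EFS analysis will be conducted once the pre-specified number of events have been reported".
- Section 9.5.2 provides a blinded review before the primary analysis: "If the rate of events is slower than anticipated, the sponsor may propose an increase in sample size".

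Section 9.4.3 puts EFS first in the secondary testing hierarchy, ahead of relapse-free and overall survival.

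**The concern.** A reader of Section 9.2 would take it that the planned trial yields 124 EFS events, and so 80% power, within 60 months of starting. A control hazard of 0.231 per year leaves nearly a third of placebo subjects event-free after five full years, and the ENTO hazard leaves half. From 180 subjects that looks too few events, even before allowing for staggered entry.

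EFS opens the secondary hierarchy and its analysis waits for a fixed event count. If that count is unlikely within the stated time, the stated power or the stated timing is wrong. If the study can also close before the count is reached, the confirmatory EFS analysis has no defined trigger.

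**Working it through.** **Inputs from Section 9.2.** Two-year control EFS 63%; hazard ratio 0.6; two-sided alpha 0.05; power 80%; 90 per arm (198 subjects in total at the 10% allowance). Accrual and dropout are not stated. I assume uniform accrual over 0 to 3 years (4 where noted) and no dropout unless given.

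**Hazards.** Placebo: -ln(0.63)/2 = 0.2310 per year, as stated. ENTO: 0.6 × 0.231 = 0.1386 per year.

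**Step 1: reproduce the 124 events.** (1.960 + 0.842)² = 7.849.

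- Schoenfeld: 4 × 7.849 / (ln 0.6)² = 120.3, so 121 events.
- Freedman: (1.6/0.4)² × 7.849 = 125.6, so 126 events.
- Power at 124 events: Φ(√124 × 0.5108/2 - 1.960) = 81% (Schoenfeld); Φ(√124 × 0.25 - 1.960) = 80% (Freedman).

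So 124 events for 80% power is right.

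**Step 2: expected events at 60 months in total.** With instant accrual, each arm gives 90 × (1 - e^(-λ×5)):

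- Placebo: 90 × (1 - e^(-1.155)) = 61.6.
- ENTO: 90 × (1 - e^(-0.693)) = 45.0.
- Total: 106.6. This is a ceiling, because accrual time and dropout only lower it.

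With accrual over A years inside total time T, each arm gives 90 × [1 - (e^(-λ(T-A)) - e^(-λT))/(λA)]. At T = 5:

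| Accrual (assumed) | Placebo + ENTO | Total | Power (Schoenfeld) | Placebo:ENTO | N for 124 events |
|---|---|---|---|---|---|
| Instant | 61.6 + 45.0 | 106.6 | 75% | 1.37 | 209 |
| 1 year | 58.1 + 41.7 | 99.8 | 72% | 1.39 | 224 |
| 2 years | 54.0 + 38.1 | 92.1 | 69% | 1.42 | 242 |
| 3 years | 49.1 + 34.2 | 83.3 | 64-65% | 1.44 | 268 |

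A Lakatos-type numerical log-rank calculation agrees: 74.8%, 68.3% and 63.9% for instant, 2- and 3-year accrual. At 198 subjects with instant accrual the total is 117.3.

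**Step 3: the 70/54 split.** The ratio is 70/54 = 1.30. Rounding can raise it to at most 1.32 (70.5/53.5 = 1.318 to the nearest integer; 70/53 = 1.321 if both arms were rounded up). Under 1:1 allocation the sample size cancels from this ratio, and the ratio falls as follow-up lengthens. Within 60 months it is never below 1.37. Solving back for common follow-up:

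- Placebo: -ln(1 - 70/90)/0.231 = 6.51 years (78.1 months).
- ENTO: -ln(1 - 54/90)/0.1386 = 6.61 years (79.3 months).

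The two arms agree closely, so the figures look like 90 per arm followed for about six and a half years.

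**Step 4: the Section 4.3 cutoff, five years after the last subject.** Using T = A + 5:

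| Accrual (assumed) | Placebo + ENTO | Total | Power (Schoenfeld) | Simulated chance of ≥124 events |
|---|---|---|---|---|
| 1 year | 64.7 + 48.0 | 112.7 | 77% | 4% |
| 2 years | 67.3 + 50.7 | 118.0 | 79% | 19% |
| 3 years | 69.5 + 53.2 | 122.7 | 81% | 45% |

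- An assumed 2% annual dropout lowers the totals to about 108, 112 and 117.
- A 4-year accrual without dropout would give 126.9.
- With 198 subjects and no dropout the totals are 123.9, 129.8 and 135.0 for 1-, 2- and 3-year accrual, and the chance of 124 events is 53%, 83% or 96%.
- Expecting 124 events by this cutoff needs about 198, 189 or 182 subjects for 1-, 2- or 3-year accrual.

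**Step 5: time to 124 expected events from 180 subjects.** About 78.8 months in total with instant accrual, 91.1 with 2-year accrual and 97.6 with 3-year accrual.

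**The case against.** **The EFS analysis is event-driven.** This stands. Nothing forces an analysis at month 60, so the 64-75% power figures describe the stated duration, not a scheduled analysis. At the Section 4.3 cutoff power is 77-81%, close to the claim. But Section 9.2 still states a duration that does not deliver its event count, and Section 4.3 can close the study first.

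**Section 9.5.2 allows a sample-size increase to reach the events.** This stands in part. If 124 events by month 60 is what was anticipated, events would run slow and the review could be used. It is optional, though, and tied to a slower rate than planned, whereas this gap arises at the planned rate. It also does not say what happens if the study ends short of the target.

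**The EFS sentence does not name 180 subjects.** True, and about 209 to 268 subjects would give 124 events in 60 months. The split rules this reading out, because 70/54 cannot occur within 60 months at any size.

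**The source of the error is not proven.** This stands. Five years after the last subject with 36-month accrual gives 69.5 and 53.2, which become 70 and 54 if each is rounded up, and it agrees with Section 4.3. Other combinations also give 70/54, such as 24 months of accrual plus 66 of follow-up. All of them total well over 60 months. The match is one consistent explanation, no more.

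**Constant hazards do not match the endpoint rule.** Section 9.4.3 says "Subjects who experience ITF will be treated as events at Day 1". This is correct, and the totals above are therefore indicative. It does not rescue the 60 months. With a Day-1 failure fraction q and two-year EFS held at 63%, placebo survival at five years is 0.63 × e^(-3λ). Any q above zero lowers λ, so placebo events fall below 61.6.

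**Conclusion.** The statement is wrong as written. The event count and its power reproduce; the 60-month total duration is incompatible with them. On the plan's own hazards the ceiling at 60 months is 107 expected events and about 75% power for 180 subjects, or 117 events for 198. With assumed 1- to 3-year accrual it is 100 to 83 events and about 72% to 64-65% power. The ceiling and the split argument need only the stated hazards, 1:1 allocation and exponential EFS; they do not depend on the accrual assumption.

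The shortfall at the Section 4.3 cutoff (about 113 to 123 expected events) does depend on it: it is small at 3-year accrual without dropout and disappears at 4 years.

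Primary-endpoint power is unaffected. SAP Section 4.2 records termination with 15 randomized subjects, and SAP Section 6.4 drops the protocol-defined efficacy analyses. What needs correcting is the design statement and any later use of it, not a pending result.

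**What to change.** Choose one of two corrections in Protocol Section 9.2 and SAP Section 4.2:

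- **(a)** Bring the duration into line with Section 4.3 (five years after the last subject). State the sample size, accrual and dropout behind the 124 events, and the expected events and power at that cutoff. For 180 subjects with 1- to 3-year accrual and no dropout these are about 113-123 events and 77-81%.
- **(b)** Keep 60 months in total and restate about 83-107 events and 64-75% power.

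Re-run the projection with a Day-1 induction-failure fraction before fixing replacement numbers, since those above assume constant hazards.

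In either case, add a sentence to Section 9.5.4 saying what is done if 124 events have not been reported when Section 4.3 ends the study.

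The cost is wording in three sections and one re-run. Under (a) the stated time to the EFS answer lengthens, to about 96 months with 36-month accrual. Under (b) the stated power falls.
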